4.1.2 Exclusion Criteria

1. Treatment with any medications contra-indicated with mIBG scanning as listed in Appendix 4. For example, decongestants containing pseudoephedrine, phenylpropranolamine and phenylephrine, sympathomimetics, cocaine, antihypertensives, tricyclic antidepressants. These drugs should be stopped before administration as indicated in this list (usually for four biological half-lives to allow almost complete wash-out but refer to list). The Investigator should seek prospective approval of any planned variation from this list from the responsible Nuclear Medicine Consultant, CI and sponsor Medical Advisor.
2. Stage 4S neuroblastoma as defined by the INSS.

CONFIDENTIAL

3. Any anti-cancer treatment planned between the routine [¹²³I]mIBG imaging and the [¹²⁴I]mIBG PET/CT scan on Day 2. Anti-cancer treatments can be started only after the Off-Study assessment on Day 3 to Day 7, see schedule of assessments in Section 7. N.B. Patients should not be enrolled in the study if their participation will delay their subsequent treatment for neuroblastoma.
4. Female patients who are pregnant or lactating.
5. At high medical risk because of non-malignant systemic disease including active uncontrolled infection.
6. Known to be serologically positive for Hepatitis B, Hepatitis C or Human Immunodeficiency Virus (HIV).
7. Patients with known hypersensitivity to mIBG.
8. Any other condition which in the Investigator's opinion would not make the patient a good candidate for the clinical study.

4.1.3 Clinical Criteria for [¹²⁴I]mIBG imaging

The patient must fulfil the following clinical criteria prior to administration of [¹²⁴I]mIBG Solution for Injection due to the limited clinical experience with this novel radiotracer.

1. One or more disease foci observed on conventional [¹²³I]mIBG planar scintigraphy. Disease foci will initially be identified by a Nuclear Medicine physician at the investigational site.
2. ≥ 3kg at the time of the [¹²⁴I]mIBG imaging to agree with the paediatric EANM guidelines.
3. Haematological and biochemical indices within the ranges shown below.

Laboratory Test	Value required for patients ≤16 years old	Value required for patients >16 years old
Haemoglobin	≥ 7.0 g/dl (N.B. transfusions will be allowed)	≥ 8.0 g/dl (N.B. transfusions will be allowed)
Absolute neutrophil count (ANC)	≥ 0.2 x 10 ⁹ /L (N.B. G-CSF support will be allowed)	≥ 0.5 x 10 ⁹ /L (N.B. G-CSF support will be allowed)
Platelet count	≥ 10 x 10 ⁹ /L (N.B. transfusions will be allowed)	≥ 50 x 10 ⁹ /L (N.B. transfusions will be allowed)
Serum bilirubin	≤ 2.5 x upper limit of normal (ULN)	≤ 2.5 x upper limit of normal (ULN)
Alanine amino-transferase (ALT), aspartate amino-transferase (AST), and/ or alkaline phosphatase (ALP)	≤ 5 x ULN	≤ 5 x ULN
	Calculated creatinine clearance using revised Schwartz formula ≥ 60 mL/min/1.73m ²	Estimated Glomerular Filtration Rate (eGFR) ≥ 60 mL/min/1.73m ²

4. Menarchal female patients must have a negative serum or urine pregnancy test before administration of [¹²⁴I]mIBG Solution for Injection on Day 1 and agree to use two highly effective forms of contraception (oral, injected or implanted hormonal contraception and condom, have an intra-uterine device and condom, diaphragm with spermicidal gel and condom) to be effective from Day 1 and for 7 days afterwards.
5. Male patients with partners of child-bearing potential must agree to take measures not to father children by using one form of highly effective contraception [condom plus spermicide] from Day 1 and for 7 days afterwards. Male patients with pregnant or lactating partners must agree to use barrier method contraception (e.g. condom plus spermicidal gel) to prevent exposure to the foetus or neonate.

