1.2 STUDY DESIGN

This is a multi-centre, non-therapeutic Phase I/II study directly comparing [¹²⁴I]mIBG PET/CT and conventional [¹²³I]mIBG imaging in patients with newly diagnosed, relapsed or refractory metastatic neuroblastoma. A minimum of 9 (if stopped after interim analysis) or 33 evaluable patients will be scanned at two centres in the UK.

Patients will be those who require routine conventional [¹²³I]mIBG planar scintigraphy as a means of assessing response to their ongoing treatment or for staging of their disease. The majority of patients will also be planned to undergo 3D imaging by SPECT where this is available. Eligible patients will undergo the planned routine [¹²³I]mIBG imaging as part of this study. These routine [¹²³I]mIBG planar scintigraphy findings will be reported by a Nuclear Medicine physician at the investigational site and will be used to confirm suitability for the subsequent novel [¹²⁴I]mIBG PET/CT imaging prior to administration of the novel [¹²⁴I]mIBG Solution for Injection.

The [¹²⁴I]mIBG PET/CT imaging will take place approximately 3-21 days after routine [¹²³I]mIBG imaging and before the commencement of any new anti-cancer therapy. Patients who fulfil the clinical criteria for [¹²⁴I]mIBG imaging in Section 4.1.3 will receive one injection of [¹²⁴I]mIBG and undergo imaging with [¹²⁴I]mIBG PET/CT the following day. Patients who do not fulfil these criteria will be withdrawn from the study. [¹²⁴I]mIBG PET/CT imaging undertaken as part of the clinical study will not affect the management or delay the commencement of new anti-cancer therapy of patients recruited to this study.

[¹²⁴I]mIBG PET/CT imaging data from the first patient will be analysed immediately by the Investigators to assess whether the scanning equipment specifications and scanning methodology are effective. The methodology will be adapted as required to ensure the quality of subsequent imaging data. Adaptations may also be made to resolve any practical and logistical issues with the events schedule for the next patient. Recruitment to the study will be competitive between centres. There is no minimum time interval required between patients.

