The majority of patients treated for neuroblastoma will have [¹²³I]*m*IBG scintigraphy using 3D SPECT over the chest and abdomen in addition to planar scintigraphy of the full body. The imaging review performed for the assessment of the primary objective will be repeated to read and score lesions identified by the available [¹²³I]*m*IBG SPECT. The number of positive lesions identified by SPECT will be used to meet the secondary objective of comparison of [¹²⁴I]*m*IBG PET/CT with [¹²³I]*m*IBG scintigraphy with 3D SPECT.

The imaging review will then be repeated to read and score all the available conventional imaging taken together including [¹²³I]*m*IBG planar and SPECT scintigraphy and cross sectional imaging with CT and MRI.

[Redacted]

[Redacted]

[Redacted]

[Redacted]

[Redacted]

[Redacted]

[Redacted]

[Redacted]

[Redacted]

[Redacted]

[Redacted]

[Redacted]

[Redacted]

[Redacted]

[Redacted]

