1.4 PATIENT GROUP

A minimum of 9 (if stopped after interim analysis) or 33 evaluable patients aged over 1 year, with histologically proven neuroblastoma with stage 4 disease (as defined by the International Neuroblastoma Staging System (INSS)), will be entered into the study. A patient must have a minimum of 1 neuroblastoma lesion identified on routine conventional [¹²³I]mIBG planar scintigraphy to be evaluable for the primary objective.

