There is a strong rationale for research aimed at improved imaging modalities employing mIBG, which is the only sensitive and specific tumour imaging biomarker available for neuroblastoma. There are currently a number of initiatives to rationalise the evaluations involved in staging neuroblastoma and identifying response to therapy, and mIBG scanning is pivotal and essential to these. Although other imaging modalities have been investigated as possible alternatives to mIBG scanning including technetium-99m bone scintigraphy, SPECT, [¹⁸F]FDG PET/CT and others, these have failed to achieve a significant overall improvement in neuroblastoma imaging. Although superior to planar scintigraphy, SPECT has several disadvantages which are that resolution still remains relatively poor and the quantification of uptake is difficult. SPECT or SPECT/CT imaging is also time-consuming, with a single body region taking up to 30 minutes; which is a particular problem in children as they are less able to comply with lying still for extended periods of time than adults.

For other tumours apart from neuroblastoma, [¹⁸F]FDG (fluorine-18 radiolabelled fluorodeoxyglucose) PET/CT's unique ability to synthesise structural and metabolic information has established its routine use for staging and post treatment assessment. It is also very rapid, with the entire body being imaged in 20 minutes in the latest scanners. However, [¹⁸F]FDG, unlike mIBG, is not a tumour-specific biomarker and suffers from poor specificity in neuroblastoma as a result. Iodine-124, as a positron emitting radiotracer with a long half-life, offers the potential to take full advantage of the high sensitivity and specificity of mIBG in conjunction with the excellent spatial and anatomical resolution offered by PET/CT.

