12.2.2 Statistical Analysis of Secondary Endpoint

The proportion of positive lesions detected by routine [¹²³I]mIBG imaging using 3D SPECT which are also identified as positive using [¹²⁴I]mIBG PET/CT will be calculated. An exact one-sided binomial test of the null hypothesis that this proportion is not more than 90% will be performed, using an alpha of 0.05 to define significance.

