2.1 Definition of Analysis Sets

The following trial populations have been defined for reporting purposes:

- Full Analysis Population: All patients enrolled to the study.
- Safety [^{123}I]mIBG Population: All patients who receive [^{123}I]mIBG (these patients may or may not have received [^{124}I]mIBG).
- Safety [^{123}I]mIBG and [^{124}I]mIBG Population: All patients who receive both [^{123}I]mIBG and [^{124}I]mIBG.
- Evaluable Population: Patients who received both [^{123}I]mIBG and [^{124}I]mIBG and underwent trial scanning with both agents. All lesions from these patients are considered independent of one another.
- [REDACTED]
- A sensitivity analysis will be informed in those in the evaluable population and have less than 10 lesions.

The primary analysis set will consist of all patients consented to the study, with at least one positive lesion recorded on routine [^{123}I]mIBG planar scintigraphy, who have also completed [^{124}I]mIBG PET/CT within 3 to 21 days as planned i.e. the Evaluable Population. Patients who did not undergo both [^{123}I]mIBG planar scintigraphy and [^{124}I]mIBG PET/CT will be excluded from this set, as will any patient where zero positive lesions were found on [^{123}I]mIBG planar scintigraphy, and patients with more than 21 days between [^{123}I]mIBG and [^{124}I]mIBG scans.

The safety analysis set for the secondary objective will consist of all patients consented to the study who received any dose of [^{124}I]mIBG at any time whether or not they subsequently completed any of the planned imaging procedures i.e. the Safety [^{123}I]mIBG and [^{124}I]mIBG Population. Additionally, all AEs occurring post consent and prior to [^{124}I]mIBG will be summarised (including those occurring post [^{123}I]mIBG administration).

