4.2.2 Secondary endpoints

SIOPEN numbers of positive lesions will be compared between [¹²⁴I]mIBG PET/CT vs. [¹²³I]mIBG planar scintigraphy+SPECT, using the same methodology and populations as for the primary endpoint.

The primary analysis and the above secondary analysis will be re-analysed using the CURIE score.

Safety and toxicity, are reported using descriptive statistics and line listings only, using the safety population

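### The SPECT comparison inherits the planar-lesion requirement, so its result applies only to planar-positive patients and may drop patients with complete SPECT and PET/CT data

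*Combined protocol and SAP*

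**What the plan says.** **Entry to PET/CT.** Protocol 4.1.3 item 1 requires "One or more disease foci observed on conventional [¹²³I]mIBG planar scintigraphy", identified first by a nuclear medicine physician at the site. The section justifies its criteria by the limited clinical experience with the tracer. Footnote f of the schedule of events holds back the Day -7 to 1 assessments until the planar scan shows a lesion. Protocol 1.2 adds: "Patients who do not fulfil these criteria will be withdrawn from the study".

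**Evaluability.** Protocol 1.4 asks for a planar lesion only for a patient "to be evaluable for the primary objective". Protocol 3.2 defines evaluability for the primary imaging analysis and for toxicity; it has no rule for SPECT.

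**SPECT endpoint.** Protocol 12.2.2 analyses "The proportion of positive lesions detected by routine [¹²³I]mIBG imaging using 3D SPECT which are also identified as positive using" PET/CT. Nothing there limits it to planar-positive patients or to lesions also seen on planar.

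**Analysis sets.** The Evaluable Population bullet in SAP 2.1 asks only that both agents were given and both scans done. The paragraph after the bullets requires at least one positive planar lesion, lists exclusions, continues "as will any patient where zero positive lesions were found on" planar scintigraphy, and equates the result with the Evaluable Population. SAP 4.2.2 then runs the SPECT comparison "using the same methodology and populations as for the primary endpoint".

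**SPECT against planar.** Protocol 2.1: "Although superior to planar scintigraphy, SPECT has several disadvantages". Protocol 1.2 describes the usual examination as "using 3D SPECT over the chest and abdomen in addition to planar scintigraphy of the full body".

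**The concern.** A requirement that belongs to the planar endpoint decides who counts in the SPECT endpoint. The protocol regards SPECT as the better of the two routine techniques, so patients with disease on SPECT and none on planar are plausible. The first secondary objective is worded for SPECT in general: PET/CT should find as many lesions or more. As planned, the estimate describes only patients with a planar focus, and neither the objective, the analysis section nor the SAP says so.

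A second loss is avoidable. The entry rule uses one site read. Consensus positivity is stricter: protocol 9.1 needs all observers to agree, and SAP 4.2.1 needs a consensus confidence score of 4 or 5. A patient can pass the site read, complete SPECT and PET/CT, and then have no consensus planar lesion. SAP 2.1 does not say which read it means. If it means consensus, that patient leaves the SPECT comparison for a reason unrelated to SPECT.

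**Working it through.** **1. The plan's own figures.** Rule: of 50 lesions, stop for futility at 45 or fewer and for efficacy at 50; final success at 96 or more of 100.

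- Early efficacy at 97%: 0.97^50 = 0.218 (plan: 22%).
- Early futility at 90%: P(X ≤ 45, n = 50) = 0.569 (plan: 57%).
- Overall success: 0.822 at 97% (plan: 82%) and 0.0266 at 90% (plan: 0.03).

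All four reproduce. They concern the planar endpoint only and are unaffected by this point. No lesion number or power is given for SPECT.

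**2. What the planar-zero exclusion does to each ratio.** SAP 4.2.1 uses Σ min(n123, n124) / Σ n123. A patient with n123 = 0 adds 0 to the numerator and 0 to the denominator, so the exclusion cannot move the primary estimate. The SPECT analogue is Σ min(nS, n124) / Σ nS, with nS the positive count on the SPECT comparator. A planar-zero patient with nS > 0 adds nS to the denominator and anything from 0 to nS to the numerator. The exclusion can therefore move only the SPECT estimate.

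**3. Who is lost.**

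| Patient | PET/CT done | In the SPECT set |
|---|---|---|
| Planar lesion at site and consensus, plus SPECT-only lesions | Yes | Yes; all SPECT-positive lesions count |
| Planar focus at site, none at consensus, SPECT-positive | Yes | Yes under the SAP 2.1 bullet; no under the later paragraph if it means consensus |
| No planar focus at site, SPECT-positive | No, withdrawn | No |

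**4. Size, on assumptions.** Let f be the share of SPECT-positive lesions lying in excluded patients, q the PET/CT agreement in those lesions, and a the agreement in retained patients. The documents give neither f nor q. Agreement over all SPECT-positive lesions is (1 − f)·a + f·q, so the overstatement is f·(a − q).

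With a = 0.97, the plan's expected agreement for planar, the overstatement in percentage points is:

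| q | f = 2% | 5% | 10% | 20% |
|---|---|---|---|---|
| 0.97 | 0 | 0 | 0 | 0 |
| 0.90 | 0.14 | 0.35 | 0.70 | 1.4 |
| 0.80 | 0.34 | 0.85 | 1.7 | 3.4 |
| 0.70 | 0.54 | 1.35 | 2.7 | 5.4 |

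Overall agreement falls to the 90% null only when f = 0.07 / (0.97 − q): 41% for q = 0.80 and 26% for q = 0.70.

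Now set agreement over all SPECT-positive lesions at exactly 90%, so that a = (0.90 − f·q) / (1 − f). For f = 10% and q = 0.70, a = 0.83 / 0.90 = 0.922. Borrowing 100 lesions from the planar design, success needs 96 at alpha 0.025 or 0.05, since P(X ≥ 95) = 0.058 and P(X ≥ 96) = 0.024 at 90%.

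| f, q | Retained-set agreement | P(success) |
|---|---|---|
| No exclusion, or q = 0.90 | 90.0% | 2.4% |
| 2%, 0.80 | 90.2% | 2.7% |
| 5%, 0.80 | 90.5% | 3.4% |
| 10%, 0.70 | 92.2% | 10% |
| 10%, 0.60 | 93.3% | 20% |
| 10%, 0.97 | 89.2% | 1.3% |

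The last row shows that the direction reverses once q exceeds agreement in the retained patients.

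**The case against.** **The hard lesions are mostly kept.** A faint SPECT-only lesion stays in the denominator if its patient has one planar focus anywhere. This stands. A reader might infer that the SPECT agreement is estimated without the lesions hardest to detect. The documents do not support that: such lesions may be under-represented, but they are not absent.

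**The direction is not established.** A reader might also infer that agreement is biased upward. The protocol's own expectation runs the other way: it credits PET/CT with better spatial resolution than SPECT and precise localisation of small foci (2.1 and 2.6). This stands too; both size and sign are open.

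**f may be small.** Every patient has stage 4 disease, planar covers the whole body, and SPECT covers only part of it. SAP 4.2.2 names planar plus SPECT as the comparator, which adds planar lesions to the denominator and lowers f further. This argues for the left-hand columns of the first table, although no figure confirms it.

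**The bullet already includes the fully scanned patients.** On the bullet alone, yes. The later paragraph contradicts it, so the SAP must say which applies.

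**The addendum changed the analysis.** It moves this objective to analysis per skeletal segment, with soft tissue separate, and adds sensitivity and specificity against a combined read. It does not redefine the population or state the restriction.

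**The entry rule has a reason.** Limited experience with the tracer is given in 4.1.3. Who receives a research tracer is a clinical and radiation-exposure decision for the sponsor, and nothing here asks for it to change.

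**Conclusion.** The point holds as one of scope and definition on a secondary endpoint. The SPECT agreement is conditional on patients with a site-read planar focus, no section says so, and SAP 2.1 gives two incompatible descriptions of the Evaluable Population that SAP 4.2.2 inherits. Under one of them, patients with complete SPECT and PET/CT data leave the SPECT analysis, while the same exclusion does nothing for the primary ratio.

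Under the assumed ranges with 97% agreement in retained patients, the overstatement is 0 to 5.4 percentage points, and it becomes an understatement if q exceeds 97%. Those figures rest on assumed f and q; the false-success rates also rest on a borrowed count of 100 lesions and on independent lesions. They show sensitivity to the unknowns and do not estimate a bias. The primary analysis and its operating characteristics are untouched.

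**What to change.** 1. In SAP 2.1, reconcile the Evaluable Population bullet with the paragraph that follows it, and say whether a recorded planar lesion means the site read or the consensus read.
2. In SAP 2.1 and 4.2.2, define a separate SPECT analysis set: SPECT done, PET/CT completed within the existing 3 to 21 day window, and at least one consensus-positive lesion on the SPECT comparator, whatever the consensus planar count.
3. State with the SPECT objective and conclusion that the result applies to patients with at least one site-read planar focus. No set definition can recover patients who never had PET/CT.
4. Report how many patients were withdrawn for having no planar focus, how many of those had SPECT, and how many had a SPECT focus. SAP 4.1 already asks for exclusions to be explained, so this adds a few counts from routine reports.

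The cost is wording and tabulation, with no added scans or exposure and no effect on the primary result. The SPECT claim becomes narrower. Because the addendum follows a review of the statistical report, the new set should be labelled as defined after that review and shown beside the existing analysis.

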4.2 PATIENT ENROLMENT

Recruitment to the study will be competitive between centres. There is no minimum time interval required between patients after review of the imaging data from the first patient.

Informed Consent from the patient's parent or guardian is required for all patients under 16 years old. Written or verbal assent will be sought from all patients under 16 years old. Informed consent is required for all patients aged 16 or older. All patients for whom informed consent has been provided must be added to the study clinical database via the electronic data capture (EDC) system by the site staff. This includes those patients who fail screening and do not go on to be enrolled on the study. Through this process a screening number will be automatically allocated for all consented patients.

The Investigator or designated representative should determine the eligibility of the patient during Screening. The Investigator should inform the Clinical Study Manager (CSM) at the Centre for Drug Development (CDD) of the outcome of the Screening assessment. Eligible patients must be enrolled in the study clinical database by completing the Enrolment and date of Pre-study i.e. Screening visit. A subject number will be automatically allocated to eligible patients. The patient will be registered by the CSM at the CDD as sponsor. The CSM will send confirmation of the patient registration by email to the Investigator after which the patient can start the thyroid blockade.

5 DOSE AND ADMINISTRATION

5.1 [¹²³I]mIBG DOSE AND ADMINISTRATION

[¹²³I]mIBG will be administered according to the current SPC. The radioactive dose will be selected according to the EANM dosage card for paediatric patients and according to the SPC for adult patients.

5.2 [¹²⁴I]mIBG DOSE AND ADMINISTRATION

5.2.1 Selection of the Dose of radioactivity to be administered

The proposed activities to be administered have been calculated based on previous studies with iodine-124 and on the calculation of activities that would deliver a similar effective dose to that delivered by a standard diagnostic [¹⁸F]FDG PET scan but greater than that delivered by an [¹²³I]mIBG scan. It is proposed to administer activities of [¹²⁴I]mIBG of 50 MBq for adult patients and paediatric patients will be scaled appropriately according to the EANM dosage card (Lassmann, Biassoni et al. 2007) such that the absorbed dose will be less than that of a [¹³¹I]mIBG scan.

To date the relatively few clinical studies using [¹²⁴I] have been restricted to adults and have largely been limited to dosimetry studies for ablation or therapy of thyroid cancer. As yet there are no guidelines regarding recommended administered doses of radioactivity. Phan *et al.* administered 74 MBq for diagnostic imaging of advanced thyroid cancer (Phan, Jager et al. 2008), Freudenberg *et al.* administered 24 to 100 MBq of [¹²⁴I]NaI to predict absorbed doses delivered to lung metastases from thyroid cancer (Freudenberg, Antoch et al. 2008), and Sgouros *et al.* administered 74 to 158 MBq for a similar purpose (Sgouros, Kolbert et al. 2004). In a two patient study of [¹²⁴I]mIBG imaging for radionuclide therapy treatment planning for adult neuroendocrine tumours, 22 MBq and 40 MBq were administered (Ott, Tait et al. 1992).

